Participating surgeons from these five centres routinely perform high-risk oncological or vascular surgery. Patients and family members are invited to participate as dyads. However, patients may participate alone while family members can only enrol with a corresponding patient. We will enrol patients in each surgeon's clinic according to a stepped wedge design implemented in six 4-month waves over a 24-month period (table 1). In wave 0, all patients will receive usual care. With each subsequent wave, 8 of the 40 enrolled surgeons will cross over into the intervention group. Once a surgeon has entered the intervention arm, all patients scheduled to see that surgeon in clinic to discuss a new surgical problem will receive the QPL intervention. We will audio-record the surgeon–patient conversation in clinic, and patients and family members will complete questionnaires at three subsequent predefined time points. In addition, we will perform qualitative interviews with a subset of participants who experienced serious postoperative complications.

Participants

Attending surgeons at participating sites who routinely perform high-risk vascular (peripheral, neurological or cardiovascular) or oncological operations on older patients will be invited to participate. Eligible patients are age 65 years and older with one or more chronic health conditions who have an outpatient consultation with a study-enrolled surgeon to discuss a new surgical problem. The surgical problem must be vascular or oncological in nature and could be treated with one of the 227 ICD-9-coded procedures our research group previously defined as high risk.⁵⁰ For each enrolled patient, we will approach one family member to participate who is present during the conversation with the surgeon in clinic. Eligible participants must be English-speaking or Spanish-speaking and able to converse with the surgeon without an interpreter (aside from Spanish-speaking participants who may use an interpreter), have self-reported visual acuity and literacy skills sufficient to read a newspaper, and be able to provide written informed consent. Patients who do not have a problem that can be potentially treated with

[figure not shown]

Figure 3 Screening, recruitment, enrolment and data collection points for patients in the control and intervention arms at each site.

surgery, for example an aneurysm that does not meet size guidelines for operative repair, will be excluded based on chart review or previsit determination by the surgeon.

Recruitment

At each study site, all eligible surgeons will receive an invitation via e-mail by the site principal investigator. Surgeons who do not opt out will be chosen first based on surgical subspecialty to capture variability in high-risk procedures and second by random selection of surgeons within a given subspecialty. Surgeons will not receive incentives for participation. We aim to enrol 40 surgeons in total, with the number of surgeons selected to be approximately proportional to the surgical volume at each site.

Study staff will review the clinic schedule of each enrolled surgeon and identify eligible patients based on chart review and clinic intake forms. On the day of clinic, study staff will meet with interested patients and family

members to explain the study and obtain informed consent prior to the conversation with the surgeon. Patients and family members will receive financial incentives valued at \$55 for participation. To avoid over-representation of any one surgeon, after each surgeon has two patients enrolled within the 4-month wave, recruitment will cease for that surgeon's patients until the next wave begins. We aim to enrol a total of 480 patients across all five sites, with 12 patients per surgeon.

We will use stratified purposeful sampling to identify a subset of enrolled patients (and family members, if applicable) who underwent surgery and experienced a serious postoperative complication, as determined by chart review. Serious complications include prolonged hospitalisation (more than 8 days postoperatively), prolonged length of stay in intensive care (greater than 3 days), prolonged mechanical ventilation, myocardial

Table 2 Primary and secondary outcome measures (items in bold are primary outcomes)

Construct	Specific measure	Source	Timing
Aim 1: Patient engagement			
Engagement in decision making	
 ▶ Number and type of questions using a predefined coding scheme ▶ OPTION 	Audio recording	Clinic visit
Self-efficacy in patient-physician interactions	
 ▶ PEPPI-5 (perceived efficacy) ▶ HCCQ (autonomy support) 	Patient and family member	First questionnaire
Aim 2: Psychological well-being and treatment received			
Concerns and well-being	
 ▶ MyCaW (self-identified concerns and well-being) 	Patient and family member	First to second First to third questionnaires
Post-treatment regret	
 ▶ 'Looking back, is there anything about your treatment that you would do differently?' 	Patient and family member	Third questionnaire
Psychological well-being (patient)	
 ▶ PROMISPsychosocial Illness Impact-Neg 4a ▶ Psychosocial Illness Impact-Pos 4a ▶ Anxiety 4a 	Patient	Second and third questionnaires
Psychological well-being (family)	
 ▶ PROMISSF Global Health ▶ Anxiety 4a 	Family member	Second and third questionnaires
Treatment received	
 ▶ Total number of operations scheduled after visit with surgeon ▶ Total number of operations scheduled and performed 	Chart review	Clinic visit Third questionnaire

HCCQ, Health Care Climate Questionnaire; MyCaW, Measure Yourself Concerns and Wellbeing; OPTION, Observing Patient Involvement score; PEPPI-5, Perceived Efficacy in Patient-Physician Interactions; PROMIS, Patient-Reported Outcomes Measurement Information System; SF, short form.

infarction, major cerebral vascular accident, new-onset dialysis or death.^{12 38} We will invite these patients and family members to participate in a face-to-face qualitative interview within 30 days after surgery. We will continue to interview patients until we reach saturation, meaning that data from subsequent transcripts become redundant with developed concepts. We anticipate this will occur with a sample of approximately 20 patients per study arm based on previous studies.^{18 21}

Randomisation and blinding

Surgeons will be stratified by study site and randomly assigned within each site to cross over from usual care to the QPL intervention in different study waves. On study commencement, a master's level statistician established a step-wise randomisation using a computer-generated randomisation schedule for the list of enrolled surgeons by site. The schedule determined the crossover wave for each surgeon and was designed to balance transitions to the intervention arm across sites in each wave according to the design in table 1. Surgeon crossover will occur in one direction only, and each within-site change will happen once every 4 months during the 24-month duration of the study. A 2-week hiatus in data collection at the start of the crossover will be instituted in transitioning clinics to ensure patients in the intervention group have had the opportunity to receive the QPL and endorsement letter from the surgeon. Study staff will notify enrolled

surgeons prior to the upcoming crossover as the intervention is dependent on surgeon endorsement. We expect negligible contamination between study arms as the intervention requires surgeon endorsement of the QPL. Only patients whose surgeons have crossed over into the intervention arm will receive the QPL and surgeon endorsement letter in the mail prior to consultation. Although patients in the control arm may access question lists from outside sources, our prior observational studies confirm surgeons do not routinely endorse the use of question prompts.

Whereas surgeons are not blinded to the intervention, every effort will be made to maintain blinding for patients and family members. Participants will be told the goal of the study is to evaluate communication between surgeons and patients, but they will not be informed about the distribution of the QPL. Transcriptionists and qualitative interviewers will be blinded to the intervention status of each encounter. Study staff are tasked with assuring the QPL has been sent and providing regular reminders to the surgeon to endorse the QPL with all new patients. Study staff will not know if the patient has received the QPL at the time of enrolment but will not be blinded during data collection. In an attempt to insulate study staff from group assignment during data collection, they will strictly adhere to a script and enquire about receipt of the QPL (with all patients regardless of group assignment) 1

Table 3 Mediating variables and covariates

Construct	Specific measure	Source	Timing
Variables mediating patient engagement			
Family member present	Observation: Was a family member present during clinic visit?	Audio recording	Clinic visit
MD endorsement of QPL	Observation: no endorsement, any endorsement, extensive endorsement	Audio recording	Clinic visit
QPL intervention penetrance	To patient: 'Did you receive information in the mail to prepare you for your appointment with the surgeon?' (yes/no/uncertain)	Patient	First questionnaire
Variables mediating psychological well-being			
Surgical complications	National Surgical Quality Improvement Project definition (yes/no)	Chart review	Third questionnaire
Advance directive	New advance directive completed or prior advance directive documented in patient chart (yes/no)	Chart review	Third questionnaire
DNR	New DNR order placed or existing DNR order documented in patient chart (yes/no)	Chart review	Third questionnaire
Covariates			
Comorbid illness	Charlson comorbidity score	Chart review	Clinic visit
Indication for surgery	Patient's presenting problem	Chart review	Clinic visit
MD subspecialty	Oncology or vascular subspecialty	Surgeon	Clinic visit
MD practice intensity	Average number of operations surgeon performs monthly	Operative log	3-month lead-in
Patient insurance status	Medicare, Medicare + Supplemental, Medicare+Medicaid, other	Chart review	Clinic visit
Patient demographics	Age, gender, race/ethnicity, educational attainment, health literacy	Patient	First questionnaire
MD demographics	Languages spoken, age, gender, race/ethnicity	Surgeon	Clinic visit

DNR, do not resuscitate; MD, medical doctor; QPL, question prompt list.

day after enrolment following administration of the first questionnaire. Furthermore, data collected from chart abstraction will be reviewed by a blinded clinician for 10% of the sample to ensure accuracy of data entry.

Intervention

Our intervention consists of the QPL brochure and a letter from the patient's surgeon encouraging its use. The surgical QPL contains 11 questions to help patients and families (1) make treatment decisions in line with their values and goals, (2) anticipate and make sense of post-operative outcomes and (3) experience less postoperative conflict about treatment of serious complications. Once a surgeon has crossed over into the intervention arm, all of his or her patients with a new vascular or oncological problem will receive the QPL intervention via US mail prior to the scheduled clinic appointment. To ensure that there is sufficient time for patients to receive the QPL intervention, we will only recruit patients who have been identified as eligible at least 5 days in advance of their appointment. This timeframe will remain consistent for

both control and intervention patients as those who are scheduled more urgently may be systematically different.

Data collection

Audio recording

We plan to audio-record and transcribe verbatim one conversation between the attending surgeon, patient and accompanying family member(s). In order to capture the primary decision-making conversation, this may occur during either the first or second clinic visit depending on the usual practice pattern of each surgeon. Prior to study commencement, each surgeon will select their usual approach: either (1) treatment decisions are typically made during the first clinical encounter, or (2) treatment decisions are typically made during the second clinic visit.

Patient and family member questionnaires

After the primary decision-making conversation with the surgeon, patients and family members will receive three questionnaires. Study staff will conduct follow-up phone interviews to administer the first questionnaire

within 24–48 hours of the patient's clinic visit. Patients and family members will complete these questionnaires independently. Administration of two subsequent questionnaires will be linked to the treatment plan and administered via phone or e-mail based on patient preference. For patients who receive surgery, questionnaires will be administered at 1–2 weeks and 6–8 weeks postoperatively. For those who undergo medical management or observation, questionnaires will be given at 6–8 weeks and 12–14 weeks following the clinic visit. We deliberately chose this timing to create similar administration schedules regardless of whether the patient pursues surgery (figure 3). We allow for up to six contact attempts at each time point.

Chart review

Study staff will use chart review to record clinical data, treatments received and outcomes of treatment. Data collected will be limited to clinical information pertaining to surgical care from the initial visit through to administration of the final survey. Data collected from chart review and questionnaires will be stored using the REDCap (Research Electronic Data Capture) software hosted at the University of Wisconsin.⁵¹

Qualitative interviews

For patients who suffer serious postoperative complications, a trained interviewer from each centre will perform a face-to-face interview with the patient, if able, and/or the family member. Interviews will be audio-recorded and transcribed verbatim.

Outcomes

Aim 1: patient engagement

To assess patient engagement in decision making, we will use direct observation and patient report measured using a coding scheme established by Walczak and colleagues³⁵ and the Perceived Efficacy in Patient–Physician Interactions (PEPPI-5) scale as our primary outcome measures. From transcriptions of the clinic conversations, two blinded and trained coders will independently count all questions, cues and concerns mentioned by the patient and all family members, friends or other caregivers present during the conversation. Our secondary outcomes for patient engagement include the Observing Patient Involvement score^{52 53} used for the recorded conversation, and the Health Care Climate Questionnaire (HCCQ)⁵⁴ administered to patients and family members at the time of the first questionnaire 24–48 hours after the visit with the surgeon. We adapted both the PEPPI-5 and the HCCQ for use by family members (table 2).

Aim 2: psychological well-being

We selected psychological well-being as an important outcome based on feedback from our patient and family stakeholders who reported significant emotional harm; specifically they felt 'blindsided' when surgical results did not match their expectations. The primary outcome measures to assess psychological well-being are the

Measure Yourself Concerns and Wellbeing (MYCaW) and patient-reported post-treatment regret. MYCaW is a patient-reported outcome measure originally designed for patients with cancer and their family members, which we have adopted for use with patients who have vascular disease. MYCaW allows patients and family members to identify their own most pressing health concerns and rate their well-being. We will administer the MYCaW at the three time points. Patients and family members will report their initial responses to the MYCaW at the time of the first questionnaire, 24–48 hours after the clinic visit. Participants will independently rescore their initial concerns and well-being at the two subsequent time points corresponding to the second and third questionnaires; the difference in scores describes improvement or deterioration in their well-being. To assess treatment-associated regret, we will ask patients and family members at the time of the third and final questionnaire — 'Looking back, is there anything about your treatment/your family member's treatment that you would do differently?' — and transform responses into a dichotomous variable (regret, no regret) for analysis.⁵⁵ We will also analyse these responses qualitatively.

Secondary outcome measures include validated measures from the Patient-Reported Outcomes Measurement Information System (PROMIS) to assess the psychological impact of illness from the patient's perspective.⁵⁶ Patients will receive the Psychosocial Illness Impact-Neg 4a, Psychosocial Illness Impact-Pos 4a and Anxiety 4a; family members will be asked to complete Anxiety 4a and PROMIS short form (SF) Global Health. Because studies of other interventions that support shared decision making show that in some situations informed patients elect more conservative treatment,⁵⁷ we will compare the total number of operations scheduled and performed on enrolled patients by their study surgeon between the control and intervention groups. We will also collect information about potential mediating variables and covariates described in table 3.

Aim 3: postoperative conflict

In qualitative interviews with a subset of participants who suffered a serious postoperative complication, we will use questions designed to explore the content of patient and family experience with perioperative conflict. The interview guide is structured around open-ended questions about perioperative events, including 'Tell me the story of your experience with surgery'.⁵⁸ The interviewer will follow up the respondents' narrative description with probing on the following domains: patient and family values and goals, decision making, interpersonal relationships (between surgeons and patients/family members, between treating physicians and between family members) and intrapersonal conflict (relating to post-treatment regret and self-blame). We will use feedback during concurrent coding and analysis to prompt additional questioning on emerging themes and trends.

Planned analyses

Quantitative analyses

Our primary analysis will compare the effectiveness of the QPL intervention relative to usual care in regard to patient engagement and patient psychological well-being. We will use an intention-to-treat analysis with all available data from participants based on group assignment. The intervention effect will be tested in the framework of generalised linear mixed-effects models^{59 60} with a treatment dummy variable, surgeon random effect and site-by-time dummy variables to control for site-specific secular trends. We will use linear mixed-effect models for continuous responses such as self-efficacy (PEPPI-5) and well-being (MYCaW), logistic random-effects models for binary responses such as post-treatment regret, and log-linear random-effect models for count-dependent variables such as the number and type of questions asked during the preoperative visit. For linear models, we will adjust for prespecified covariates to increase the statistical precision of our treatment effect estimation.

Our secondary analyses will examine other patient endpoints such as psychological well-being (PROMIS measures) and nature of treatment received. These analyses will also test for intervention effects in family member outcomes such as PEPPI-5, HCCQ, MYCaW, post-treatment regret and psychological well-being. We will use the generalised linear mixed modelling framework used in primary analyses for these outcomes. All models will be estimated and tested using PROC MIXED or PROC NLMIX in SAS V.9.3.

We will perform additional analyses to test and quantify whether and to what extent the effect of the QPL intervention on patient engagement outcome measures is mediated by the presence of a family member during the visit with the surgeon. Exploratory analysis of family-reported outcomes will occur independently of patient-reported outcomes. To accomplish this, we will compare the indirect effect with the total effect in joint linear structural equation models for the endpoint and the mediator, including correlated random surgeon effects for each of the mediator and endpoint parts of the models. In addition, we anticipate treatment effect could vary across subpopulations defined by the following covariates: indication for surgery, patient comorbid illness and insurance status. Therefore, we will test the effect of treatment separately in subpopulations defined by these variables.

To decrease missing data, we limited the number of questions in the follow-up questionnaires and will provide a bonus incentive for participants who complete all three questionnaires. At the time of analysis, we will develop a comprehensive description of the missingness patterns and develop a plan for imputation that leverages the available data and concentrates on the data most heavily subject to missingness. If data are missing on predictor variables of interest, values will be imputed using multiple imputation techniques (ie, chained equations imputations).^{61 62} If dropout is substantial, we will again use

multiple imputation, including exploiting responses from the first two time points (day of clinic visit and 24–48 hours postvisit), to impute responses from the final two questionnaires, to maximise statistical efficiency and to minimise bias.

Sample size and power calculation

Each arm will contain 240 patients, for a total of 480 patient participants. Based on our prior work, we expect about 70%–80% of patients will have a family member present who will participate. Therefore, we estimate 384 family members from all sites will partake, although we will enrol up to 480 family members if all patients have a family member interested in participating. Assuming all enrolled patients enrol with a family member, the maximum number of all possible participants (surgeons, patients and family members) is 1000.

For each quantitative aim, we desire a family-wise two-sided type I error rate of $\alpha=0.05$; under a Bonferroni correction, tests will be conducted with nominal $\alpha=0.05/2=0.025$ because there are two primary endpoints for aim 1 and aim 2 (table 2). Using patient satisfaction data at one site, we found that between-surgeon variance accounts for only 5% of the total variance. Because power in the stepped wedge design is slightly degraded with greater variance between (vs within) surgeons, we assumed a worst-case scenario between-surgeon variance of 30%. We interpreted this as the interclass correlation between multiple patients of the same surgeon at a given site and included a surgeon-level random effect in our calculation, anticipating between 5% and 30% of the total variance to be accounted for by surgeon effects (ie, interclass correlation (ICC) =0.05–0.30). Extending the information-based method of computing power for a basic stepped wedge design⁴⁹ to the case of our multisite stepped wedge design, we custom-programmed power calculations using R V.3.2.1 (R Foundation for Statistical Computing).

With this method, we computed power of 82% to detect small-to-medium and 93% to detect medium effect sizes of Cohen's $d=0.425$ and $d=0.5$, respectively. Assuming the SD for PEPPI-5 within each treatment arm is 4.3,⁶⁴ we will have 93% power to detect effects as small as 2.15 points. For the number of patient questions, we assumed a mean difference of 1.4 questions between arms.⁴⁰ Assuming overdispersion of two relative to Poisson data, within arm SD=2.7, yielding $d=1.4/2.7=0.52$, which we are well powered to detect. For the MYCaW well-being scale, Jolliffe *et al*⁶⁵ found SD=1.26 at 6 weeks, and a 6-week versus baseline mean difference of 0.59. We will also have 93% power to detect an MYCaW difference as small as $0.5\times1.26=0.63$, comparable with the difference over time in Jolliffe *et al*.⁶⁵ For regret, we assume the upper bound risk of the presence of regret is 0.3,⁵⁵ yielding SD=0.46; we will have over 90% power to detect a regret risk difference of 0.23. Nearly identical power results were obtained via a continuous latent liability model for a binary event (regret).⁶⁶ To account for clustering within sites, this

calculation includes fixed effects terms for site, time (wave) and site-by-time, reflecting our a priori analysis plan.

Qualitative analysis

We will use directed content analysis⁶⁷ to compare interpersonal and intrapersonal conflict between study arms as it relates to the phenomenon of surgical buy-in.^{28 32 68} To gain understanding of the trajectory of each patient's story, we will triangulate data sources by linking the audio tape of the surgeon–patient decision-making conversation and the patient's clinical history from chart review with the follow-up interview. We have previously shown that surgeons see preoperative conversations as a significant event, a time when a two-way agreement is made whereby the surgeon commits to operating and the patient commits to endure potentially burdensome postoperative care.²⁸ We will use this understanding of surgical buy-in to code and analyse preoperative clinic visits and postoperative interview transcripts with the goal of understanding how the contractual relationship that surgeons perceive is experienced by patients. We will explore how postoperative complications were discussed during the initial patient–surgeon interaction with and without the QPL and whether this interaction has impact on subsequent treatment decisions, interpersonal and intrapersonal conflict.

ETHICS AND DISSEMINATION

Ethical review

All participants will provide written informed consent and may withdraw from the study at any time without affecting the medical care they receive from the clinical team. For surgeons, study participation will not affect their professional standing. Institutional review board approval has been granted at each of the five sites, and a Certificate of Confidentiality has been granted in order to offer enrolled surgeons protection from legal demands, such as subpoenas and court orders for study data. Identifying information on recorded transcripts will be redacted prior to analysis, and all audio recordings and hard copies of data will be destroyed after analysis is complete and manuscripts are submitted. The aims of the study meet the criteria for minimal risk. We will follow accepted adverse event monitoring procedures including regular review by the Data Monitoring Committee.

Relevance and dissemination

The design of the QPL intervention addresses important gaps in preoperative communication between surgeons and older adults facing a decision about high-risk surgery. The results of this study will inform our understanding of how interventions to confront interactional barriers between doctors and patients affect patients' capacity to participate and share in decision making. The engagement of a variety of stakeholders and incorporation of deeply held concerns of patients and families into the development of the QPL are strengths that create potential

for significant impact. Furthermore, should we find the intervention superior to usual care, it is inexpensive and easily scalable to facilitate widespread dissemination in all outpatient clinics where high-risk surgery is considered. We anticipate these results will be generalisable to other surgical settings as well as encounters for patients who have been referred specifically for discussion of other types of treatment, for example in medical or radiation oncology clinics.

Efficacy, however, is contingent upon a letter of endorsement from the surgeon that accompanies the QPL brochure. Furthermore, durable changes in surgeon behaviour as a result of questions and attitudes the QPL engenders in their patients may contribute to the effectiveness of the intervention over time. As such, our dissemination strategies will be targeted primarily at surgeons. We have support of leadership at the American College of Surgeons (ACS) and anticipate dissemination through various ACS portals, including the National Surgical Quality Improvement Program and the Coalition for Quality in Geriatric Surgery, as well as distribution of the intervention and description of the implementation processes on the ACS website. In addition, based on feedback from our patient and family advisors who felt dissemination of results to patients and families is critically important, we will provide study updates and distribute study results via a study website. We plan to present study results at the annual ACS Clinical Congress and local chapter meetings. We plan to publish the main trial outcomes in a peer-reviewed journal. We will follow the CONSORT reporting standards for pragmatic⁶⁹ and cluster-randomised⁷⁰ trials. Study results will be released to participating surgeons, patients, families and the general medical community.

Author affiliations

¹Department of Surgery, University of Wisconsin, Madison, Wisconsin, USA

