The intervention effect will be tested in the framework of generalized linear mixed effects models^{42,43} with a treatment dummy variable, surgeon random effect and site-by-time dummy variables to control site-specific secular trends.

All models will be estimated and tested using SAS version 9.3 (SAS Institute, Cary, NC), specifically PROC MIXED and PROC NLMIX.

We do not plan to impute missing data if the rate of missingness is low. Currently, our rate of missingness is quite low: 97% of patients and 92% of family members have completed T1. For T2, 88% of patients and 86% of family members have completed the survey and for T3 87% of both patients and family members have completed their survey. We plan to exclude variables for which there is no response (rather than impute these variables). Although we have a small number of incomplete audio recordings, we will treat audio recordings where less than half of the encounter with the surgeon was captured (a total of 6 recordings) as completely missing and those with more than half recorded as complete. We will perform sensitivity analysis to test whether this small loss of data impacts our findings by comparing the outcomes with and without inclusion of audio recordings that are more than half complete.

Aim-1 primary outcomes [Question Counting, PEPPi-5]

Aim 1 has five primary outcomes and as such will be analyzed with a Type I error rate of $\alpha=0.01$.

For question counting, we consider four specific types of questions and evaluate them with ordinal categories:

- Number of OPTIONS questions asked by patients and family members (0, 1, 2+)
- Number of EXPECTATION questions asked by patients and family members (0, 1, 2+)
- Number of ADVANCE DIRECTIVES questions asked by patients and family members (0, 1+)
- Number of RISKS questions asked by patients and family members (0, 1, 2+)

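### The only power figures stated for PEPPI-5 (82% and 93%) belong to alpha 0.025 and 480 patients; the per-protocol PEPPI-5 test at alpha 0.01 on about 430 has no stated power, and by recalculation has about 65-70% and 82-86%

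*Combined protocol and SAP*

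**What the plan says.** **Published protocol, Sample size and power calculation.** The plan fixes the error rate first: "For each quantitative aim, we desire a family-wise two-sided type I error rate of" 0.05. It then splits this to 0.025 per test, "because there are two primary endpoints for aim 1 and aim 2 (table 2"). The sample is stated without an allowance for non-response: "Each arm will contain 240 patients, for a total of 480 patient participants". On that basis, "we computed power of 82% to detect small-to-medium and 93% to detect medium effect sizes", namely d=0.425 and d=0.5. The 93% is then expressed as 2.15 PEPPI-5 points (SD 4.3) and 0.63 MYCaW points (SD 1.26).

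**SAP, Aim-1 primary outcomes.** "Aim 1 has five primary outcomes and as such will be analyzed with a Type I error rate of" 0.01. The five are four question types and PEPPI-5. PEPPI-5 is analysed as a continuous score in a linear mixed model. The four question types are ordinal or binary.

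**SAP, General Analysis Plan.** Non-responses are left out and not imputed while missingness stays low. Interim completion by patients is 97% at T1, when PEPPI-5 is collected. For the later survey, "For T2, 88% of patients and 86% of family members have completed the survey".

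**SAP, Updated analysis plan and modified power analysis.** Realised enrolment is 222 control and 221 treatment patients. Power is recomputed for the four question types (alpha 0.0125) and for regret (alpha 0.05), and the text describes the power as still robust. PEPPI-5 and MYCaW are left out of the recalculation because they are no longer regarded as valid primary outcomes. The modified analysis is described as additional to the per-protocol one.

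**The concern.** The per-protocol section keeps a PEPPI-5 test whose alpha and sample both differ from those behind its power figure. Alpha fell from 0.025 to 0.01 because the question outcome was split into four types. The sample fell from 480 to about 430. The update restates power only for other outcomes, so the published article is the only source from which a reader can attach a power to the PEPPI-5 test.

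A null per-protocol PEPPI-5 result could then be read against 93% power (or 82% for the smaller effect) that the written test does not have at those standardised effects. For d=0.425 the chance of missing a true effect would be 30-35%, not 18%.

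**Working it through.** **Inputs**
- Layout (published protocol, Table 1): 40 surgeons, 5 sites, 6 waves, 8 surgeons crossing over in each of waves 1 to 5.
- Model: "calculation includes fixed effects terms for site, time (wave) and site-by-time, reflecting our a priori analysis plan", plus a treatment term and a surgeon random intercept.
- Surgeon ICC: "anticipating between 5% and 30% of the total variance to be accounted for by surgeon effects".
- Planned sample: 480, or 2 patients per surgeon per wave (40 × 6 × 2).
- Realised sample: 222 + 221 = 443. With 97% T1 completion, 443 × 0.97 ≈ 430 for PEPPI-5.

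**Method.** The standard error (SE) of the treatment effect comes from the generalised least squares information matrix with 30 site-by-wave fixed effects and total variance 1. Patients are spread evenly over the 240 surgeon-waves. Power = Φ(d/SE − z), with z = 2.241 for two-sided alpha 0.025 and z = 2.576 for alpha 0.01.

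**Step 1. Reproduce the plan's figures (480 patients, alpha 0.025).**

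| ICC | SE | d=0.425 | d=0.5 |
|---|---|---|---|
| 0.05 | 0.134 | 82.4% | 93.2% |
| 0.10 | 0.137 | 80.7% | 92.1% |
| 0.20 | 0.136 | 81.3% | 92.5% |
| 0.30 | 0.131 | 84.5% | 94.4% |

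For ICC 0.05: 0.425/0.134 − 2.241 ≈ 0.93, and Φ(0.93) ≈ 82%. The printed figures are therefore right for this design. Alpha 0.05 (87-90% and 95-97%), alpha 0.01 (70-75% and 86-90%) and an unclustered comparison (99.2% and 99.9%) all fail to give 82%/93%.

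**Step 2. Change alpha only (480 patients, alpha 0.01).** 70-75% for d=0.425 and 86-90% for d=0.5.

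**Step 3. Use the written PEPPI-5 test (430 patients, alpha 0.01).**

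| ICC | SE | d=0.425 | d=0.5 |
|---|---|---|---|
| 0.05 | 0.1406 | 67.2% | 83.6% |
| 0.10 | 0.1435 | 65.0% | 81.8% |
| 0.20 | 0.1425 | 65.8% | 82.4% |
| 0.30 | 0.1372 | 69.9% | 85.7% |

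The lowest values, near ICC 0.13, are 64.7% and about 81.5%. Losing patients at random across surgeon-waves, and not evenly, gives 64-69% and 81-85%.

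**Step 4. Check without the layout.** The stated 82% at d=0.425 implies SE = 0.425/(0.915 + 2.241) = 0.1346. Scaling by √(480/430) gives 0.1422. At alpha 0.01 power is then 66.0% for d=0.425; the same steps from the 93% give 82.7% for d=0.5.

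**Step 5. PEPPI-5 in raw points.** The SAP reports a blinded IQR of 20-24. If scores are roughly normal, SD ≈ 4/1.349 = 2.97, so 2.15 points is d = 2.15/2.97 = 0.72. At 430 patients and alpha 0.01, power is 99.3-99.7%. With SD 3.5 it is 95.5-97.1%, with SD 3.8 it is 91-94%, and with the plan's SD of 4.3 it is 82-86%.

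**Step 6. MYCaW.** Its alpha is 0.025 in both places, so only the sample changes: 443 × 0.88 ≈ 390. The written analysis is of T1-to-T2 change, so its power depends on the T1-T2 correlation r, which the documents do not give. If 1.26 is taken as the SD at each time, the SD of change is 1.26 × √(2(1 − r)). For 0.63 points, power is about 55-59% at r=0, 86-89% at r=0.5 and 98-99% at r=0.7. No single figure can be defended.

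**The case against.** **The SAP has moved on.** Before unblinding, the team set PEPPI-5 aside for ceiling effects and said that even a significant difference would lack clinical meaning. It reappears among the secondary outcomes, and MYCaW becomes a stratified analysis. This stands and lowers the stakes. It does not remove the point: the per-protocol section still prescribes both tests, and the modified plan is presented as an addition.

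**The printed PEPPI-5 claim is in points and may still hold.** This stands in part. With the blinded SD near 3.0, power for 2.15 points exceeds the printed 93%. That estimate assumes rough normality under a ceiling, and the 333 participants behind the IQR may include family members. It shows that the SD of 4.3 also needs revisiting.

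**A reader might infer that all five Aim 1 tests have 65-70% and 82-86% power.** The documents do not support that. Four of the five are ordinal or binary, are tested by logistic models, and have power stated separately on an odds-ratio scale. A standardised mean difference does not describe those tests.

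**A reader might also infer a replacement figure of 86-89% for MYCaW.** That figure holds only at a T1-T2 correlation of 0.5, which appears nowhere in the documents.

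**The inputs are imprecise.** The plan does not say which ICC produced 82%/93%, and its worst case of 0.30 gives somewhat higher power in this model. The completion rates are interim. The results are therefore given as ranges; across the whole ICC range, power for d=0.425 is at most about 70%.

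**Conclusion.** The point holds for PEPPI-5. The 82% and 93% are internally correct for two-sided alpha 0.025 and 480 complete patients, so this is not an arithmetic error. It is a power statement left in place after the alpha and the sample changed. At the plan's SD, the per-protocol PEPPI-5 test has about 65-70% power for d=0.425 and 82-86% for d=0.5, a loss of roughly 12-17 and 7-11 percentage points against the printed figures.

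This rests on the Table 1 layout, ICC 0.05 to 0.30 and 97% T1 completion. In raw points, power for 2.15 could be about 99% if the SD is near 3.0. For MYCaW, the documents support only the statement that its 93% assumed 480 complete patients.

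The matter is minor. Power for d=0.5 stays above 80%, and the modified plan no longer treats either outcome as a valid primary.

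**What to change.** - Next to the per-protocol PEPPI-5 test, state power at alpha 0.01 and the realised number of responders: with about 430, 65-70% for d=0.425 and 82-86% for d=0.5.
- Say there that the 82%/93% in the published protocol applied to alpha 0.025 and 480 complete patients.
- Give the detectable PEPPI-5 difference in points from the SD computed on the blinded data, in place of 4.3.
- For MYCaW, say that the 93% assumed 480 complete patients, and rerun power for the T1-to-T2 change model with the blinded SD of change.
- Do not attach these standardised-difference figures to the four question types.
- State which plan, per-protocol or modified, is confirmatory.

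The cost is a short paragraph in the SAP and a rerun of the existing R power program. Stated power for PEPPI-5 becomes less favourable on the standardised scale. Nothing changes in the conduct of the trial.
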